 - Bowdle VAS Internal and External Perceptions composite scores (E_{max})
 - Drug Similarity VAS 12-hour postdose scores
- Pupillometry
 - Maximum pupil constriction as assessed by the difference between initial pupil diameter and minimum pupil diameter (MPC)

	
 ○ Time to maximum pupil constriction ○ Pupillometry area over the curve (time-averaged pupillometry area over the effect curve relative to baseline [TA_PAOC]) 																				
Investigational Product, Dose, and Mode of Administration:	
Kratom 500 mg capsules Manufacturer: Sun Distribution, Super Organics Mode of administration: Oral
																				
Placebo and Mode of Administration:	
Placebo-to-match kratom 500 mg capsules Mode of administration: Oral
																				
Study Population:	Healthy, male and female nondependent, recreational polydrug users with opioid experience																				
Planned Number of Subjects:	A total of 40 subjects (8 subjects in each of the 5 cohorts) will be included.																				

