In addition to the requirement that subjects be “history qualified” (i.e., have a history of recreational opioid use), medical history and clinical assessments will also be used to confirm that subjects meet the required study eligibility criteria and to confirm that they are not dependent on drugs or alcohol. Urine drug screens and alcohol checks, as well as other assessments (e.g., pregnancy tests) will be used to confirm compliance and eligibility.

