4.1. Inclusion Criteria

1. Provision of signed and dated informed consent form (ICF)
2. Stated willingness to comply with all study procedures and availability for the duration of the study
3. Healthy adult male or female

4. Current nondependent, polydrug recreational user who has used opioid drugs for recreational (nontherapeutic) purposes (i.e., for psychoactive effects) at least 10 times in the subject's lifetime and at least once in the last 12 weeks from Screening; and has a history of recreational use of at least 2 or more of any of the perception-altering (e.g., lysergic acid diethylamide [LSD], kratom, cannabis, dronabinol, ketamine, phencyclidine [PCP], dextromethorphan, 3,4 methylenedioxymethamphetamine [MDMA], mescaline, psilocybin, tryptamine derivatives or ring-substituted amphetamines with perception altering effects) or stimulant (e.g., cocaine, amphetamine, methamphetamine, methylphenidate, methcathinone, and other synthetic cathinones) drugs on at least 5 occasions in the subject's lifetime
5. If male, meets one of the following criteria:
 - a) Is able to procreate and agrees to use one of the accepted contraceptive regimens and not to donate sperm from study drug administration to at least 90 days after study drug administration. An acceptable method of contraception includes one of the following:
 - Abstinence from heterosexual intercourse
 - Double-barrier method (e.g., male condom with spermicide or male condom with a vaginal spermicide [gel, foam, or suppository])
 - Or
 - b) Is unable to procreate; defined as surgically sterile (i.e., has undergone a vasectomy at least 180 days prior to study drug administration)
6. If female, meets one of the following criteria:
 - a) Is of childbearing potential and agrees to use an acceptable contraceptive method. Acceptable contraceptive methods include:
 - Abstinence from heterosexual intercourse from the Screening visit through to at least 30 days after study drug administration
 - or
 - One of the following contraceptive methods, used from at least 28 days prior to the Screening visit through to at least 30 days after study drug administration:
 - Systemic contraceptives (combined birth control pills, injectable/implant/insertable hormonal birth control products, or transdermal patch)
 - Intrauterine device (with or without hormones)
 - Male partner vasectomized at least 6 months prior to the Screening visit
 - or

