13. Presence of clinically significant ECG abnormalities at the Screening visit, as defined by medical judgment. Note: QT corrected according to Fridericia's formula (QTcF) interval of > 450 msec in male subjects or > 470 msec in female subjects will be exclusionary. The ECG may be repeated once for confirmatory purposes if the initial value obtained exceeds the limits specified.
14. Estimated glomerular filtration rate (eGFR) \leq 60 mL/min as calculated by the CKD-EPI equation
15. Any clinically significant illness in the 28 days prior to study drug administration
16. Use of any prescription drugs (with the exception of hormonal contraceptives or hormone replacement therapy) in the 28 days prior to study drug administration, that in the opinion of an Investigator would put into question the status of the participant as healthy
17. Use of St. John's wort in the 28 days prior to study drug administration
18. Positive test result for alcohol and/or drugs of abuse at admission (prior to study drug administration). Subjects with positive results at admission may be rescheduled at the discretion of an Investigator. If tetrahydrocannabinol (THC) is positive at admission a cannabis intoxication evaluation will be done by an Investigator and subjects may be permitted to continue in the study at the discretion of an Investigator. Other positive test

results should be reviewed to determine if the subject may be rescheduled, in the opinion of the investigator.

19. Positive screening results to HIV Ag/Ab combo, hepatitis B surface antigen or hepatitis C virus tests
20. Any other clinically significant abnormalities in laboratory test results at Screening that would, in the opinion of an Investigator, increase the subject's risk of participation, jeopardize complete participation in the study, or compromise interpretation of study data
21. Inclusion in a previous group for this clinical study
22. Intake of kratom in the 14 days prior to study drug administration
23. Intake of an Investigational Product (IP) in the 28 days prior to study drug administration
24. Donation of plasma in the 7 days prior to study drug administration
25. Donation of 1 unit of blood to American Red Cross or equivalent organization or donation of over 500 mL of blood in the 56 days prior to study drug administration
26. Subject cannot eat dairy and/or is lactose intolerant

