6.3.1. Pupillometry

Pupillometry will be used as an objective physiological PD measure as it is a sensitive measure of central opioid action and appears to be resistant to tolerance development with repeated administration. An electronic pupillometer will be used to measure pupil diameter. Pupil diameter will be measured as outlined in [Table 6-1](#) and is further detailed in [Table 6-9](#). Data from a series of frames will be used in the calculation, and the final display will show the weighted average and standard deviation (SD) of the pupil size. Measurements will be collected under mesopic lighting conditions. For each subject, every effort will be made to use the same

eye for all assessments throughout the study. The pupillometry assessments will be completed immediately prior to the administration of all other PD measures.

Table 6-9. Pupillometry Schedule

Pupillometry - Scheduled Time Points
Day 1: predose and 0.5, 1, 1.5, 2, 2.5, 3, 4, 6, 8, 10, and 12 hours postdose
Day 2: 24 hours postdose

Windows for timed pupillometry measurements are presented in [Table 6-10](#).

Table 6-10. Acceptable Windows for Timed Pupillometry Measurements

Elapsed Time	Accepted Window
Predose (Day 1)	Within 60 minutes prior to study drug administration
Postdose	Within 5 minutes following collection of PK blood sample

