15. APPENDIX 6: CLINICAL LABORATORY EVALUATIONS

Clinical Laboratory Test Panel	Description
General biochemistry:	Alanine aminotransferase, albumin, alkaline phosphatase, anion gap, aspartate aminotransferase, bilirubin total, blood urea nitrogen (BUN), BUN/creatinine ratio, calcium, carbon dioxide, chloride, creatinine, (including eGFR calculated using the CKD-EPI equation), glucose, phosphorus, potassium, protein total, sodium, and uric acid
Lipid profile:	Total cholesterol, cholesterol high-density lipoprotein, cholesterol low-density lipoprotein and triglycerides
Endocrinology:	FSH ^a
Hematology:	White cell count with differential (absolute values of neutrophil, lymphocyte, monocyte, eosinophil, and basophil), red cell count, hemoglobin, hematocrit, mean corpuscular hemoglobin, mean corpuscular hemoglobin concentration, mean corpuscular volume, and platelet count, red cell distribution width
Serology:	HIV Ag/Ab Combo, Hepatitis B surface antigen and Hepatitis C virus
Urinalysis:	Color, clarity, specific gravity, pH, leukocyte, protein, glucose, ketones, bilirubin, blood, nitrite, urobilinogen. Microscopic examination will only be performed if the dipstick test is outside of the reference range for leukocyte, blood, nitrite or protein
Urine drug screen:	Amphetamines, barbiturates, benzodiazepines, cocaine, fentanyl, MDMA, opiates, oxycodone, phencyclidine, and tetrahydrocannabinol,
Pregnancy test:	Serum pregnancy test at Screening only and urine pregnancy test at all other scheduled days
Alcohol screen:	Urine alcohol test

Abbreviations: eGFR = estimated glomerular filtration rate; FSH = follicle-stimulating hormone; HIV = human immunodeficiency virus.

a. Performed for females in a postmenopausal state only.

**16. APPENDIX 7: COLUMBIA-SUICIDE SEVERITY RATING SCALE (C-SSRS) –
BASELINE/SCREENING VERSION**

COLUMBIA-SUICIDE SEVERITY RATING SCALE (C-SSRS)

Baseline/Screening Version

Version 1/14/09

Posner, K.; Brent, D.; Lucas, C.; Gould, M.; Stanley, B.; Brown, G.; Fisher, P.; Zelazny, J.; Burke, A.; Oquendo, M.; Mann, J.

Disclaimer:

This scale is intended to be used by individuals who have received training in its administration. The questions contained in the Columbia-Suicide Severity Rating Scale are suggested probes. Ultimately, the determination of the presence of suicidal ideation or behavior depends on the judgment of the individual administering the scale.

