**Table 10-1 Clinical Laboratory Assessments**

Clinical Laboratory Test Panel	Description
General biochemistry:	Alanine aminotransferase, albumin, alkaline phosphatase, anion gap, aspartate aminotransferase, bilirubin total, blood urea nitrogen (BUN), BUN/creatinine ratio, calcium, carbon dioxide, chloride, creatinine, (including eGFR calculated using the CKD-EPI equation), glucose, phosphorus, potassium, protein total, sodium, and uric acid
Lipid profile:	Total cholesterol, cholesterol high-density lipoprotein, cholesterol low-density lipoprotein and triglycerides
Endocrinology:	FSH a
Hematology:	White cell count with differential (absolute values of neutrophil, lymphocyte, monocyte, eosinophil, and basophil), red cell count, hemoglobin, hematocrit, mean corpuscular hemoglobin, mean corpuscular hemoglobin concentration, mean corpuscular volume, and platelet count, red cell distribution width
Serology:	HIV Ag/Ab Combo, Hepatitis B surface antigen and Hepatitis C virus
Urinalysis:	Color, clarity, specific gravity, pH, leukocyte, protein, glucose, ketones, bilirubin, blood, nitrite, urobilinogen. Microscopic examination will only be performed if the dipstick test is outside of the reference range for leukocyte, blood, nitrite or protein
Urine drug screen:	Amphetamines, barbiturates, benzodiazepines, cocaine, fentanyl, MDMA, opiates, oxycodone, phencyclidine and tetrahydrocannabinol
Pregnancy test:	Serum pregnancy test at Screening only and urine pregnancy test at all other scheduled days
Alcohol screen:	Urine alcohol test

Abbreviations: eGFR = estimated glomerular filtration rate; FSH = follicle-stimulating hormone; HIV = human immunodeficiency virus.

a. Performed for females in a postmenopausal state only.

The following listings will be presented:

- All laboratory values by category
- Out-of-range laboratory values
- Clinically significant laboratory values

For protocol-specified laboratory parameters, summary tables on observed and change from baseline values will be presented by treatment and visit for each category, including biochemistry (including lipid profile), hematology, and urinalysis (quantitative data only).

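### The urine drug screen has no methadone line, so an opioid that the protocol itself names may go unassayed at admission

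*Protocol*

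**What the plan says.** **The panel.** Protocol Appendix 6 gives the urine drug screen as "Amphetamines, barbiturates, benzodiazepines, cocaine, fentanyl, MDMA, opiates, oxycodone, phencyclidine, and tetrahydrocannabinol". SAP Table 10-1 repeats it: "Amphetamines, barbiturates, benzodiazepines, cocaine, fentanyl, MDMA, opiates, oxycodone, phencyclidine and tetrahydrocannabinol". Neither list has methadone, and no other section of either document adds a methadone test.

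**What the panel is for.** Protocol 1.1 says: "Urine drug screens and alcohol checks, as well as other assessments (e.g., pregnancy tests) will be used to confirm compliance and eligibility". Exclusion criterion 18 (Protocol 4.2) acts on a "Positive test result for alcohol and/or drugs of abuse at admission (prior to study drug administration"). The schedule (Protocol Table 6-1) places the screen at Screening and on Day -1.

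**Who is enrolled.** Inclusion criterion 4 (Protocol 4.1) asks for recreational opioid use "at least 10 times in the subject's lifetime and at least once in the last 12 weeks from Screening". Methadone is one of the comparison drugs in the Drug Similarity scale (Protocol Table 6-14, SAP Table 9-6), shown to subjects with at least two lifetime uses.

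**What is measured.** Protocol 6.3.1 uses pupillometry because "it is a sensitive measure of central opioid action". The first pupil endpoint is "Maximum pupil constriction as assessed by the difference between initial pupil diameter and minimum pupil diameter (MPC"). Respiratory rate and oxygen saturation are among the primary safety measures. Protocol 1.1 says that kratom itself acts at mu opioid receptors.

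**The concern.** The population is selected for opioid use, the test product acts at the mu opioid receptor, and one of the physiological endpoints was chosen for its sensitivity to opioids. In that setting the admission screen should cover the opioids that subjects can be expected to know. The panel gives opiates, oxycodone and fentanyl separate lines. That suggests the opiates line was not meant to stand for every opioid, and methadone has no line of its own.

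A subject with methadone on board could then pass the assay. Two things are at stake. The first is safety: such a subject would receive kratom on top of another mu-opioid agonist. The second is measurement: a pupil that is already constricted before dosing has less room to constrict, so that subject's response is blunted, and the predose respiratory values are not drug-free either. With six active subjects per dose, a single subject carries visible weight.

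**Working it through.** The documents give no figure on this point, so there is none to reproduce. The check has two parts: a comparison of the relevant sections, and a scale calculation on an assumed prevalence.

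**1. Which safeguards would catch methadone?**

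- *Urine screen (Appendix 6, exclusion 18).* Exclusion 18 needs a positive result. With no methadone line, methadone can trigger it only if the opiates assay happens to detect it, and the documents do not say whether it does.
- *Ban on recreational drugs (Protocol 4.4).* It starts at Screening, which may fall anywhere from Day -28 to Day -1. Use shortly before a late Screening visit breaks no rule.
- *Washout.* Exclusions 22 and 23 set 14 days for kratom and 28 days for investigational products. No interval is stated for recreational opioids.
- *Drug use history (Protocol 6.1.2.2; Screening and Day -1).* It records drug names and date of last use. It is self-reported, and no criterion is tied to the date of last opioid use.
- *DSM-5 modules and exclusion 9.* These remove moderate to severe use disorder within 2 years, not recent occasional use.
- *Exclusion 16.* It covers prescription drugs only, and only where the investigator judges that they put healthy status in question.
- *Predose pupil size.* It is measured, but no eligibility threshold is attached to it.
- *Extra laboratory tests (Protocol 6.1.6).* Larger standard panels are allowed but not required.

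None of these is a committed assay for methadone.

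**2. Weight of one affected subject.**

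Inputs: 6 active subjects per dose, and 2 placebo subjects per cohort × 5 cohorts = 10 pooled placebo subjects (Protocol Table 3-1, SAP 9.3).

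Suppose that all six subjects in an arm would have mean constriction *d*, and that one of them shows none. The arm mean becomes 5*d*/6, a fall of 1/6 = 16.7%. This is the worst case within that set-up; partial blunting gives less. One subject is 1/10 = 10% of the pooled placebo group.

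**3. Chance of at least one affected subject.**

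The prevalence *p* of undetected methadone at admission is not in the documents and is assumed here. The formula is 1 − (1 − *p*)^*n*.

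| Assumed *p* | One 6-subject arm | All 40 subjects |
|---|---|---|
| 0.5% | 1 − 0.995^6 = 3.0% | 1 − 0.995^40 = 18.2% |
| 1% | 1 − 0.99^6 = 5.9% | 1 − 0.99^40 = 33.1% |
| 2% | 1 − 0.98^6 = 11.4% | 1 − 0.98^40 = 55.4% |
| 5% | 1 − 0.95^6 = 26.5% | 1 − 0.95^40 = 87.1% |

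The 17% effect belongs with the middle column, because it applies within one arm. The right-hand column includes the 10 placebo subjects and says only how likely the trial is to meet the problem somewhere.

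**The case against.** The strongest reply is that nothing in the documents says that the opiates assay misses methadone. That is correct. Separate lines for oxycodone and fentanyl make it likely but do not prove it, so the point is conditional.

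Table 6-14 is also a list of comparison drugs for a rating scale, not a specification for the panel. It includes caffeine, nicotine, pseudoephedrine, LSD and ketamine, which have no panel line either. This stands as far as the table goes. Methadone differs in being an opioid, in a trial that measures opioid effects. Nor does inclusion 4 imply methadone, or any opioid, on board on Day 1: one use of any opioid within 12 weeks of Screening is enough. And passing the assay is not the same as passing the whole eligibility review.

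Two stronger readings are tempting, and the documents do not support them:

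- *A reader might infer that undetected methadone confounds the kratom–placebo comparison.* Allocation is randomized 6:2 within each cohort and treatment is double-blind, so methadone use before dosing cannot depend on the assigned arm. The pupil endpoints are relative to predose, and the PD model takes baseline as a covariate where applicable (SAP 9.3). The result is noise, a blunted response or chance imbalance.
- *A reader might infer that any opioid-related adverse event in such a subject would stop escalation.* The cohort rule (Protocol 4.3.2.1.2) needs a kratom-related SAE, or moderate or severe events in at least half of the cohort. The maximum-tolerated-dose rule (Protocol 3.3) turns first on three or more subjects and is otherwise committee judgement. One non-serious event forces no stop. A single SAE attributed to kratom would suspend dosing, but that is a narrower case.

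Continuous SpO2 monitoring with an alarm (Protocol 6.1.4.2) also limits the safety consequence, though it does not prevent the exposure.

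**Conclusion.** The gap holds in a limited form. Neither panel lists methadone, the way other opioids are listed suggests that it is not covered, and no other safeguard is an assay for it. The consequence is an avoidable safety exposure and a possible loss of sensitivity in the pupil and respiratory measures, not systematic bias.

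The size depends on assumptions. The fall of at most about 17% in an arm mean supposes that the affected subject would otherwise have responded like the other five and instead shows no further constriction. The chances in the table rest wholly on assumed prevalences. The conclusion itself depends on the opiates assay not detecting methadone, which the site or laboratory can settle. The pupil endpoints are non-key secondary. This is a cheap improvement to the plan, not a flaw that threatens the trial's conclusions.

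**What to change.** Confirm with the laboratory whether the opiates assay detects methadone. If it does, say so in Protocol Appendix 6 and SAP Table 10-1. If it does not, add methadone to the urine drug screen in both places, so that exclusion 18 can act on it.

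The urine is already collected at Screening and on Day -1, so no visit, procedure or analysis changes. The cost is one more analyte and possibly a few subjects rescheduled at admission, which exclusion 18 already allows.

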## VERSION CONTROL

---

Version	Date	Author	Description of Changes
1.0	2024/01/04	[name]/ [name]/ [name]	Not applicable

## SUMMARY OF CHANGES

---

Description	Section/Location	Rationale

## ABBREVIATIONS

---

AE	Adverse Event
ANOVA	Analysis Of Variance
ARCI	Addiction Research Center Inventory
ATC	Anatomical Therapeutic Chemical
BMI	Body Mass Index
CI	Confidence Interval
CRF	Case Report Form
CSR	Clinical Study Report
C-SSRS	Columbia Suicide Severity Rating
CTCAE	Common Terminology Criteria for Adverse Events
CV%	Coefficient of Variation
DMP	Data Management Plan
DTS	Deviation Tracking System
ECG	Electrocardiogram
EOS	End of Study
ET	Early Termination
ICF	Informed Consent Form
ICH	International Conference on Harmonisation
IP	Investigational Product
LLOQ	Lower Limit Of Quantitation
ln	Natural Logarithm
MedDRA	Medical Dictionary for Regulatory Activities
Min	Minimum
Max	Maximum
NCA	Non-Compartmental Analysis
PD	Pharmacodynamic(s)
PK	Pharmacokinetic(s)
PT	Preferred Term
SAE	Serious Adverse Event
SAP	Statistical Analysis Plan
SD	Standard Deviation
SOC	System Organ Class
SOP	Standard Operating Procedure
SRC	Safety Review Committee
TEAE	Treatment-Emergent Adverse Event
TFLs	Tables, Figures, and Listings
VAS	Visual Analog Scale

## 1 INTRODUCTION

This Statistical Analysis Plan (SAP) provides a detailed description of the statistical methods and procedures to be implemented for the analyses of data from the Clinical Study Protocol 75F40121C00199. The analyses described in the SAP are based upon the final version of the Clinical Study Protocol 1.0, dated 2023/06/05.

## 2 STUDY OBJECTIVES

The objectives of the study and corresponding study endpoints are detailed in [Table 2-1](#).

**Table 2-1      Objectives and Related Endpoints**

Objective	Endpoint
Primary	
The primary objective of the study is to evaluate the safety and tolerability of single ascending oral doses of kratom relative to placebo when administered in healthy nondependent recreational polydrug users with opioid experience.	Safety will be evaluated through the assessment of adverse events (AEs), laboratory tests, vital signs (blood pressure, pulse, respiratory rate, oxygen saturation, and body temperature), electrocardiogram (ECG), physical examination findings, and Columbia Suicide Severity Rating Scale (C-SSRS).
Secondary	
To evaluate the pharmacokinetics (PK) of mitragynine, 7-hydroxy-mitragynine, paynantheine, speciogynine, and speciociliatine following single ascending oral doses of kratom in healthy nondependent recreational polydrug users with opioid experience.	The PK endpoints of this study are the following PK parameters of mitragynine, 7 hydroxymitragynine, paynantheine, speciogynine, and peciociliatine: Maximum observed concentration ( $C_{max}$ ), time of maximum observed concentration ( $T_{max}$ ), area under the concentration-time curve from time zero to the last observed concentration ( $AUC_{0-T}$ ), and area under the concentration-time curve from time zero extrapolated to infinity ( $AUC_{0-\infty}$ ). Additionally, dose-normalized PK parameters ( $C_{max}/D$ , $AUC_{0-T}/D$ , and $AUC_{0-\infty}/D$ ) will be estimated.


To evaluate the pharmacodynamics (PD) of single ascending oral doses of kratom in healthy nondependent recreational polydrug users with opioid experience.
	
The PD endpoint of this study is the maximum (peak) effect (<math>E_{max}</math>) over 24 hours for Drug Liking (“at this moment”), assessed on a bipolar (0 to 100 points) visual analog scale (VAS).
 
Key secondary PD endpoints are:
 
 
• Overall Drug Liking VAS (<math>E_{max}</math>)
 
• Take Drug Again VAS (<math>E_{max}</math>)
 
• High VAS (<math>E_{max}</math>)
 
 
Non-key secondary PD endpoints are:
 
 
• Balance of Effects 
 
○ Drug Liking VAS (minimum effect [<math>E_{min}</math>], time of maximum effect [<math>TE_{max}</math>], time of minimum effect [<math>TE_{min}</math>], and time-averaged area under the effect-time curve [TA_AUE])
 
 
 
• Positive Effects 
 
○ Good Effects VAS (<math>E_{max}</math>, <math>TE_{max}</math>, and TA_AUE)
 
○ High VAS (<math>E_{max}</math>, <math>TE_{max}</math>, and TA_AUE)
 
 
 
• Negative Effects 
 
○ Bad Effects VAS (<math>E_{max}</math>, <math>TE_{max}</math>, and TA_AUE)
 
 
 
• Other Subjective Effects 
 
○ Any Effects VAS (<math>E_{max}</math>, <math>TE_{max}</math>, and TA_AUE)
 
○ Feeling Drunk VAS (<math>E_{max}</math>, <math>TE_{max}</math>, and TA_AUE)
 
○ Drowsiness/Alertness VAS (<math>E_{max}</math>, <math>TE_{max}</math>, <math>E_{min}</math>, <math>TE_{min}</math>, and area over and under the effect-time curve [TA_AOE, TA_AUE])
 
○ Relaxation/Agitation (<math>E_{max}</math>, <math>TE_{max}</math>, <math>E_{min}</math>, <math>TE_{min}</math>, and TA_AOE, TA_AUE)
 
○ ARCI MBG Scale (<math>E_{max}</math>, <math>TE_{max}</math>, and TA_AUE)
 
○ ARCI A Scale (<math>E_{max}</math>, <math>TE_{max}</math>, and TA_AUE)
 
○ ARCI BG Scale (<math>E_{max}</math>, <math>TE_{max}</math>, and TA_AUE)
 
○ ARCI PCAG Scale (<math>E_{max}</math>, <math>TE_{max}</math>, and TA_AUE)
 
 
 

---	---

	
 
○ ARCI LSD Scale (<math>E_{max}</math>, <math>TE_{max}</math>, and <math>TA\_AUE</math>)
 
○ Bowdle VAS Internal and External Perceptions composite scores (<math>E_{max}</math>)
 
○ Drug Similarity VAS12-hour postdose scores
 
● Pupillometry           
 
○ Maximum pupil constriction as assessed by the difference between initial pupil diameter and MPC
 
○ Time to maximum pupil constriction
 
○ Pupillometry area over the curve (time-averaged pupillometry area over the effect curve relative to baseline [TA_PAOC])
 
 
 

--	--

